### 10.7 Justification of surrogate consent

According to the Belmont Report, respect for persons incorporates at least two ethical convictions; first, that individuals should be treated as autonomous agents, and second, that person with diminished autonomy are entitled to protection. One method that serves to protect subjects is restrictions on the participation of subjects in research that presents greater than minimal risks. Commentators and research ethics commissions have held the view that it is permissible to include incapable subjects in greater than minimal risk research as long as there is the potential for beneficial effects and that the research presents a balance of risks and expected direct benefits *similar* to that available in the clinical setting. Several U.S. task forces have deemed it is permissible to include incapable subjects in research. For example, the American College of Physicians' document allows surrogates to consent to research involving incapable subjects only "if the net additional risks of participation are not substantially greater than the risks of standard treatment." Finally, NBAC stated that an IRB may approve a protocol that presents greater than minimal risk but offers the prospect of direct medical benefits to the subject, provided that "the potential subject's LAR gives permission..."

Consistent with the above ethical sensibilities regarding the participation of decisionally incapable subjects in research and the previous assessment of risks and benefits in the previous section, the present trial presents a balance of risks and potential direct benefits that is *similar* to that available in the clinical setting, with the exception of the additional blood draws.

### 10.8 Additional safeguards for vulnerable subjects

The present research will involve subjects who might be vulnerable to coercion or undue influence. As required in 45CFR46.111(b), we recommend that sites utilize additional safeguards to protect the rights and welfare of these subjects. Such safeguards might include, but are not limited to: a) assessment of the potential subject's capacity to provide informed

consent, b) the availability of the LAR to monitor the subject's subsequent participation and withdrawal from the study. The specific nature of the additional safeguards will be left to the discretion of the central IRB, in conjunction with the sites.

## 10.9 Confidentiality

Federal regulations at 45 CFR 46 111 (a) (7) requires that when appropriate, there are adequate provisions to protect the privacy of subjects and to maintain the confidentiality of data. To maintain confidentiality, all laboratory specimens, evaluation forms, and reports will be identified only by a coded number. The coded number will be generated by a computer, and only the study team will have access to the codes. All records will be kept in a locked, password protected computer. All computer entry and networking programs will be done with coded numbers only. All paper case report forms will be maintained inside a locked office. Study information will not be released without the written permission of the patient, except as necessary for monitoring by the National Heart, Lung, and Blood Institute, and the PETAL Clinical Coordinating Center or their designees.

## 11 ADVERSE EVENTS

### 11.1 Safety Monitoring

Assuring patient safety is an essential component of this protocol. Each participating investigator has primary responsibility for the safety of the individual participants under his or her care. A clinical trial adverse event is defined as any untoward medical event associated with the use of a drug or study procedure in humans, whether or not it is considered related to a drug or study procedure.

The Investigators will determine daily if any adverse events occur during the period from enrollment (signing of the informed consent) through study day 14 or hospital discharge, whichever occurs first. Investigators will determine if the event is serious or related to the study drug. The rationale for this time window is the 2 week half-life of 25OHD, which helps to define the period at risk from vitamin D.

The following adverse events will be collected in the adverse event case report forms:

- Serious adverse events
- Non-serious adverse events that are considered by the investigator to be related to study drug or study procedures

Investigators will assess if there is a reasonable possibility that the study drug or procedure caused the event. Investigators will also consider if the event is explained by the patient's underlying medical conditions, anticipated clinical course, previous medical conditions, and concomitant medications.

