**Figure 2: Proposed mechanisms of vitamin D and prevent ARDS and improve clinical outcomes**

### 3.3 Recent Clinical Trials

Vitamin D deficiency is common in critically ill patients, with approximately 40-50% meeting the Institute of Medicine definition for vitamin D deficiency (25OHD levels <20 ng/mL [50 nmol/L]). Consistent with preclinical data, observational clinical studies also support that vitamin D deficiency is a common, potentially reversible risk factor for ARDS. Specifically, early vitamin D deficiency in the ED or at ICU admission is associated with higher hospital and ICU lengths of stay, lung and other organ injury, prolonged mechanical ventilation, and mortality.

Based on the rationale outlined above, several recent phase II trials have evaluated the potential of acute vitamin D repletion to improve outcomes in medical and surgical ICU. In ICU patients with sepsis, Leaf et al found that active vitamin D (calcitriol)-treated patients had increased expression of the potent antimicrobial peptide LL-37 ( $p=0.04$ ) and observed a lower mortality rate vs. placebo (17% vs. 23%;  $p=ns$ ). Dancer et al demonstrated that a 200,000 IU pre-operative vitamin D3 dose decreased post-operative extravascular lung water and pulmonary vascular permeability indices in esophagectomy patients at high risk for ARDS. Quraishi et al found that a 400,000 IU vitamin D3 dose in ICU patients with sepsis increased 25OHD levels by an average 12 ng/mL and led to increased expression of LL-37, as well as decreased pro-inflammatory cytokines (IL-1 and IL-6). Han et al found that 500,000 IU

(administered over 5 days) safely increased 25OHD levels in ventilated ICU patients and was associated a lower hospital length of stay

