### 3.6.2.3 Safety Endpoints

10. **Calcium levels to day 14:** Because the half-life of 25OHD is approximately 2 weeks, we will record clinically available serum or ionized calcium levels through day 14 for all randomized participants. In addition, we will measure baseline and day 3 in the first 300 randomized participants in real time, either as part of routine clinical care or as a research procedure if not available. Day 3 is the when 25OHD levels peak in ICU patients given 540,000 IU of vitamin D. While no prior study of acute vitamin D repletion, using similar high doses as our trial, has observed clinically important hypercalcemia, we will confirm these findings in the VIOLET trial. Because little change in calcium levels is anticipated, access to individual-level calcium results will not unblind study staff. During the trial, the DSMB may seek additional subject measurements for safety assessment, though this is not anticipated.
11. **Kidney stones to day 90:** While an association between hypervitaminosis D and kidney stones has been suggested, the relationship with high dose vitamin D supplementation and kidney stones remains controversial. We will assess for incident kidney stones by chart

review at the end of the hospitalization and by self-report at the 90 day phone call for those discharged from the hospital prior to day 90.

12. **Fall-related fractures to day 90:** The association between acute vitamin D supplementation and falls/fractures remains unclear. Most data suggest that high dose vitamin D in healthy outpatients may improve muscle function, balance, and bone mineral density, and thus decrease fall-related fractures, but other data suggest that high dose vitamin D supplementation may actually increase the incidence of falls/fractures. Because of this uncertainty and limited data in hospitalized patients, we will assess for incident fall-related fractures by chart review at the end of the hospitalization and by self-report at the 90 day phone call for those discharged from the hospital prior to day 90.

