### 6.3 Assessment during Study

We will collect the following in-hospital data by medical record review to assess trial efficacy and safety endpoints. Most data may be assessed by medical record review.

1. Duration of ventilation to day 28 (may require call to LTAC facility if hospital discharge with assisted breathing prior to day 28).
2. Organ failure assessments daily to day 7 (ARDS, creatinine, and vasopressor use), using clinically available data.

3. In-hospital vitamin D supplementation daily to day 14 (medication only, not related to dietary intake or nutritional supplementation).
4. In-hospital calcium levels daily to day 14, (required on day 3 for first 300 randomized participants, otherwise if clinically available).
5. Adverse events and serious adverse events to day 14
6. Safety endpoints (i.e., kidney stones and fall related fractures)
7. Vital status and ventilator status (among survivors) at hospital discharge
8. Date of hospital discharge or date of death, as applicable
9. Hospital discharge disposition. "Home" will be defined as pre-hospitalization level of care.

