## 9 RISK ASSESSMENT

### 9.1 Potential Risks to Subjects

As noted in Section 5, high dose enteral vitamin D appears to be safe in critically ill patients with no related adverse events reported in a recent large trial using the dose proposed for this study. As such, the potential risks below are theoretical and have not been observed in previous clinical trials.

**Hypercalcemia:** The primary risk associated with use of vitamin D supplementation is hypercalcemia, which may cause gastrointestinal symptoms, dizziness, fatigue, and less commonly cardiac arrhythmia. This risk is largely theoretical, as trials using similar vitamin D doses as in this protocol, including in ICU patients, have not observed clinically significant hypercalcemia. For example, in the largest trial to date using 540,000 IU vitamin D3 as the intervention (Amrein et al, n=475), the maximum total serum calcium level observed in the vitamin D group during the first 28 days was 11.2 mg/dL with no clinically or statistically significant difference in mean total serum or ionized calcium levels. To enhance trial safety, we will exclude patients with baseline hypercalcemia or 25OHD levels  $\geq 20$  ng/mL.

We will confirm the minimal effect of acute vitamin D repletion on calcium levels by collecting and analyzing clinically available calcium levels to day 14 (after which 25OHD levels decline). We will also measure day 3 calcium levels (after plateau of 25OHD levels) as protocol specified testing in the first 300 randomized participants, and in additional participants or timepoints if required by the DSMB or cIRB to monitor ongoing safety.

**Kidney stones:** While an association between hypervitaminosis D and kidney stones has been suggested, the relationship with high dose vitamin D supplementation and kidney stones remains controversial. However, we will exclude patients with a personal history of recent (past year) or multiple prior kidney stones and will closely monitor participants for incident kidney stones during the hospitalization and follow-up period.

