## 11.2 Serious Adverse Events

A serious adverse event is any adverse event that results in one of the following outcomes:

- Death
- A life-threatening experience (that is, immediate risk of dying)
- Prolonged inpatient hospitalization

As per <http://www.fda.gov/Safety/MedWatch/HowToReport/ucm053087.htm>: Report if admission to the hospital or prolongation of hospitalization was a result of the adverse event. Emergency room visits that do not result in admission to the hospital should be evaluated for one of the other serious outcomes (e.g., life-threatening; required intervention to prevent permanent impairment or damage; other serious medically important event).

- Persistent or significant disability/incapacity

As per <http://www.fda.gov/Safety/MedWatch/HowToReport/ucm053087.htm>: Report if the adverse event resulted in a substantial disruption of a person's ability to conduct normal life functions, i.e., the adverse event resulted in a significant, persistent or permanent change, impairment, damage or disruption in the patient's body function/structure, physical activities and/or quality of life.

Important medical events that may not result in death, be life-threatening, or require hospitalization may be considered serious adverse events when, based upon appropriate medical judgment, they may jeopardize the patient and may require medical or surgical intervention to prevent one of the outcomes listed in this definition.

Serious adverse events will be collected during the first **14 study days** or until hospital discharge, whichever occurs first, regardless of the investigator's opinion of causation. Thereafter, serious adverse events are not required to be reported unless the investigator feels the events were related to either study drug or a protocol procedure.

Study site personnel must alert the CCC of any **serious and study drug or study procedure related** adverse event within 24 hours of investigator awareness of the event. Alerts issued via telephone are to be immediately followed with official notification on the adverse event case report form. See Appendix for reporting timelines for serious, unexpected, study related events (SAEs) and serious, unexpected suspected adverse reactions (SUSARs).

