4.3 Adverse Events

Adverse events will be analyzed using weighted Poisson regression with non-serious events weighted by one and serious events weighted by two. Events rather than patients will be the unit of analysis. Adverse events will be grouped and analyzed separately by MedDRA system organ classes

References

1. Acute Respiratory Distress Syndrome The Berlin Definition The ARDS Definition Task Force JAMA. 2012;307(23):2526-2533
2. Official journal of the American society of nephrology VOLUME 2 | ISSUE 1 | MARCH 2012 <http://www.kidney-international.org>
3. Multiplicity Considerations in the Design and Analysis of Clinical Richard J. Cook and Vern T. Farewell. Journal of the Royal Statistical Society. Series A (Statistics in Society), Vol. 159, No. 1 (1996), pp. 93-110)

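### Adverse events are collected only to day 14 or discharge and compared with no term for observed time, so hospital days lost before day 14 can look like fewer events

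*Protocol*

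**What the plan says.** Protocol section 11.1 has investigators look daily for adverse events from consent "through study day 14 or hospital discharge, whichever occurs first". Section 11.2 collects serious events over the first 14 study days "or until hospital discharge, whichever occurs first, regardless of the investigator's opinion of causation"; after that, only serious events judged related must be reported. Non-serious events are collected only if judged related. Section 6.3 lists "Adverse events and serious adverse events to day 14" among data taken from the in-hospital record, and calcium to day 14 is on the same in-hospital list.

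SAP section 4.3 specifies weighted Poisson regression, with weight one for non-serious and two for serious events, run separately by MedDRA system organ class. It adds: "Events rather than patients will be the unit of analysis". No offset, person-time or other exposure term is named. SAP section 3.3.3 compares calcium daily with t-tests, and compares any hypercalcemia up to day 14 with a chi-square test.

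Hospital stay among survivors is a secondary efficacy endpoint (Protocol section 2.9). The rationale in section 3.3 cites a trial in which vitamin D "was associated a lower hospital length of stay".

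SAP section 3.1 recognises that differential recovery and mortality complicate outcomes seen only while patients are on study. It claims correct type I error under a global null in which treatment affects no patient in any way.

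**The concern.** Each participant's observation time ends at an event that treatment may move. A comparison of counts treats two arms with different observed time as if they had been watched equally long. If vitamin D patients leave hospital earlier within the 14 days, fewer events are recorded in that arm although the risk on each day is unchanged. Equal safety could then read as a safety benefit, and a modest true excess could be hidden.

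The SAP's assurance in section 3.1 does not reach this case. It is correct when treatment changes nothing, because observed time is then equal on average. Harm, however, has to be judged beside a possible benefit, and there that null fails.

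Protocol Appendix C also requires notification of the central IRB and the FDA if the DSMB finds a higher overall rate of adverse events on vitamin D, without saying what the denominator of that rate is.

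**Working it through.** No figure in the documents bears directly on this point: there is no adverse event rate, expected stay or safety power to reproduce. The only input taken from them is the 14-day cap. Everything else below is an assumption. Counts are unweighted; the 1/2 weights leave the ratio unchanged if the serious share is equal in both arms, but they affect the standard error.

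**1. Observed days with exponential stay of mean m.** Mean observed days = m(1 − e^(−14/m)). At an equal and constant daily hazard, the ratio of expected counts equals the ratio of observed days.

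| Mean stay, placebo vs vitamin D (days) | Mean observed days | Count ratio |
|---|---|---|
| 5 vs 4 | 4.70 vs 3.88 | 0.83 |
| 7 vs 6 | 6.05 vs 5.42 | 0.90 |
| 10 vs 9 | 7.53 vs 7.10 | 0.94 |
| 10 vs 8 | 7.53 vs 6.61 | 0.88 |
| 14 vs 13 | 8.85 vs 8.57 | 0.97 |
| 20 vs 19 | 10.07 vs 9.91 | 0.98 |

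A patient whose stay falls from 25 to 18 days is observed for 14 days either way: ratio 1.00.

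**2. Masking of a true excess.** With a true hazard ratio of 1.10, the expected count ratio is 1.10 × 0.942 = 1.04 for 10 vs 9 days and 1.10 × 0.877 = 0.97 for 10 vs 8 days.

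**3. Early deaths.** Let death also end observation, with discharge hazard d and death hazard q. Mean observed days = (1 − e^(−14(d+q)))/(d+q). Take d = 1/10 on placebo and assume 10% vs 7.5% dead by day 14.
- Equal discharge hazards: 7.12/6.98 = 1.02.
- Discharge hazard 1/9.5 on vitamin D: 6.92/6.98 = 0.99.
- Discharge hazard 1/9 on vitamin D: 6.70/6.98 = 0.96.

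**4. Effect on one organ-class test.** Assume 45 placebo events in a class (0.3 events per patient × 1,500 patients × 10% of events). With z = ln(ratio)/√(1/e₀ + 1/e₁), where e₀ and e₁ are the expected counts:
- 10 vs 9 days: 45 vs 42.4 events, z = −0.28; a two-sided 5% test rejects about 6% of the time.
- 10 vs 8 days: 45 vs 39.5 events, z = −0.60; it rejects about 9% of the time.

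The distortion lies mainly in the estimate. A single class will seldom be falsely significant because of it.

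**5. Is a log(observed days) offset enough?** Under constant hazard, yes: the ratio returns to 1.00. If events cluster early, no. Assume a hazard proportional to e^(−t/3), identical in both arms. Expected events are proportional to (1 − e^(−14k))/k with k = 1/3 + 1/m.
- m = 10 gives 2.302 and m = 8 gives 2.178, so the count ratio is 2.178/2.302 = 0.95.
- Dividing by the ratio of observed days, 0.946/0.877 = 1.08. The single offset turns a small false benefit into a larger false harm.

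Now split person-days P and events E by study day j, and solve ΣE₁ⱼ = Σ(E₀ⱼ + E₁ⱼ)·rP₁ⱼ/(P₀ⱼ + rP₁ⱼ) for the arm ratio r, as a Poisson model with study day would. Daily bands give r = 1.00; bands of days 0–3, 3–7 and 7–14 give r = 1.01.

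**The case against.** The best defence is that the harms specific to vitamin D mostly lie outside this model. Kidney stones and fall-related fractures are followed to day 90, related serious events stay reportable after discharge, and mortality to day 90 is the primary endpoint. Appendix C normally exempts hypercalcemia, kidney stones and falls with fracture from adverse event reporting, and SAP section 3.3.3 tests them separately. The SAP is also silent on an offset; it does not rule one out. All of this stands and limits what is at stake. It does not cover the events that do enter section 4.3, nor calcium, which is recorded only in hospital.

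Stronger readings are tempting but not supported:

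- A reader might infer that any shorter stay lowers the count. Only days lost before day 14 count, and fewer early deaths work the other way.
- A reader might infer that all toxicity follow-up ends at discharge. The day-90 endpoints and the related serious events show otherwise.
- A reader might pool all events and report a high chance of a false finding. Section 4.3 tests by organ class, where the chance is much smaller, and any such figure needs an event rate that the documents do not give.
- A reader might see a conflict between sections 6.3 and 11.1. The day-14 item in 6.3 is on a list of in-hospital data, so the two can be read together.
- A reader might set "calcium levels to day 14 (after which 25OHD levels decline" (section 9.1) against "Day 3 is the when 25OHD levels peak in ICU patients given 540,000 IU of vitamin D" (section 3.6.2.3) and call the window's rationale contradictory. Section 9.1 does not say that decline begins only then, and section 11.1 says only that the half-life helps to define the risk period. This is wording and changes no result.

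The objection that a single offset can over-correct is sound, and it shapes the fix.

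**Conclusion.** The point holds in limited form. Adverse events, and serious events not judged related, are observed to the earlier of day 14 or discharge, and the planned count comparison ignores how long each arm was observed. If vitamin D shortens stay within the first 14 days, its arm shows fewer events at the same hazard: a ratio of about 0.94 for mean stays of 10 vs 9 days and 0.88 for 10 vs 8. These figures assume exponential stay, a constant and equal daily hazard and no early deaths. The effect shrinks as stays lengthen, and with fewer early deaths the ratio can reach or pass 1. If stay does not differ between arms and early mortality is also similar, the planned comparison is sound.

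The same truncation affects daily calcium and the hypercalcemia comparison to day 14. It does not affect related serious events, kidney stones or fractures. This is a cheap improvement to the safety analysis and leaves the primary analysis untouched.

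**What to change.** In SAP section 4.3, keep the count comparison and report beside it an event-rate comparison. Use person-days from consent to the earliest of day 14, study-hospital discharge or death, with log(person-days) as the offset and study day or day bands in the Poisson model. Do not use a single offset per patient alone. Tabulate observed days by arm. Beside the hypercalcemia comparison, show by arm the number of participants with a calcium value and the number of days with one.

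Dates of discharge and death are already collected (Protocol section 6.3). The day bands need the onset day of each event; the case report form is not among the documents, but section 11.1 requires daily assessment, so I assume it is available. The cost is a little more analysis and no new data. One limit remains: the rate still assumes that patients remaining in hospital on a given day are comparable between arms, and the SAP should say so.
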